11.3 REPORTING TO HEALTH AUTHORITIES

Adverse event reporting to regulatory agencies will be done by the MAH according to local and international regulatory requirements.

Expedited reporting of serious adverse events (SAE), e.g. suspected unexpected serious adverse reactions (SUSARs) to health authorities and IECs/IRBs, will be done according to local regulatory requirements. Further details regarding this reporting procedure are provided in the ISF.

12. PLANS FOR DISSEMINATING AND COMMUNICATING STUDY RESULTS

The rights of the investigator and of the sponsor with regard to publication of the results of this study are described in the investigator contract. As a general rule, no study results should be published prior to finalisation of the Study Report.

BI intends to use data from this study to prepare peer-reviewed publications and other scientific communications such as abstracts, posters, and podiums presentations.

ANNEX 1. LIST OF STAND-ALONE DOCUMENTS

The stand-alone documents for this non-interventional study are:

- Informed Consent Form
- Statistical and Epidemiological Analysis Plan (SEAP)

The above documents will be archived in the Trial Master File in their original English master version.

ANNEX 2. ENCEPP CHECKLIST FOR STUDY PROTOCOLS

EUROPEAN MEDICINES AGENCY
SCIENCE MEDICINES HEALTH

Doc.Ref. EMA/540136/2009

European Network of Centres for
Pharmacoepidemiology and
Pharmacovigilance

ENCEPP Checklist for Study Protocols (Revision 2, amended)

Adopted by the ENCePP Steering Group on 14/01/2013

The [European Network of Centres for Pharmacoepidemiology and Pharmacovigilance \(ENCEPP\)](#) welcomes innovative designs and new methods of research. This Checklist has been developed by ENCePP to stimulate consideration of important principles when designing and writing a pharmacoepidemiological or pharmacovigilance study protocol. The Checklist is intended to promote the quality of such studies, not their uniformity. The user is also referred to the [ENCEPP Guide on Methodological Standards in Pharmacoepidemiology](#) which reviews and gives direct electronic access to guidance for research in pharmacoepidemiology and pharmacovigilance.

For each question of the Checklist, the investigator should indicate whether or not it has been addressed in the study protocol. If the answer is "Yes", the page number(s) of the protocol where this issue has been discussed should be specified. It is possible that some questions do not apply to a particular study (for example in the case of an innovative study design). In this case, the answer 'N/A' (Not Applicable) can be checked and the "Comments" field included for each section should be used to explain why. The "Comments" field can also be used to elaborate on a "No" answer.

This Checklist should be included as an Annex by marketing authorisation holders when submitting the protocol of a non-interventional post-authorisation safety study (PASS) to a regulatory authority (see the [Guidance on the format and content of the protocol of non-interventional post-authorisation safety studies](#)). Note, the Checklist is a supporting document and does not replace the format of the protocol for PASS as recommended in the Guidance and Module VIII of the Good pharmacovigilance practices (GVP).

Study title:

RealGiDo: Real-world data on Gi(l)otrif® dose adjustment in first-line treatment, TKI-naïve, advanced non-small cell lung cancer patients with EGFR activating mutations

Study reference number:

1200.270

Section 1: Milestones	Yes	No	N/A	Page Number(s)
1.1 Does the protocol specify timelines for				
1.1.1 Start of data collection ¹				11
1.1.2 End of data collection ²				11
1.1.3 Study progress report(s)				
1.1.4 Interim progress report(s)				
1.1.5 Registration in the EU PAS register				11
1.1.6 Final report of study results.				11

Comments:

¹ Date from which information on the first study is first recorded in the study dataset or, in the case of secondary use of data, the date from which data extraction starts.

² Date from which the analytical dataset is completely available.

Protocol for non-interventional studies based on existing data

BI Study Number 1200.270

c09038525-01

Proprietary confidential information © 2016 Boehringer Ingelheim International GmbH or one or more of its affiliated companies

Section 2: Research question	Yes	No	N/A	Page Number(s)
2.1 Does the formulation of the research question and objectives clearly explain:				
2.1.1 Why the study is conducted? (e.g. to address an important public health concern, a risk identified in the risk management plan, an emerging safety issue)				12,13
2.1.2 The objective(s) of the study?				14
2.1.3 The target population? (i.e. population or subgroup to whom the study results are intended to be generalised)				15,16
2.1.4 Which formal hypothesis(-es) is (are) to be tested?				
2.1.5 If applicable, that there is no a priori hypothesis?				13,18

Comments:

--

Section 3: Study design	Yes	No	N/A	Page Number(s)
3.1 Is the study design described? (e.g. cohort, case-control, randomised controlled trial, new or alternative design)				15
3.2 Does the protocol specify the primary and secondary (if applicable) endpoint(s) to be investigated?				14
3.3 Does the protocol describe the measure(s) of effect? (e.g. relative risk, odds ratio, deaths per 1000 person-years, absolute risk, excess risk, incidence rate ratio, hazard ratio, number needed to harm (NNH) per year)				19

Comments:

--

Section 4: Source and study populations	Yes	No	N/A	Page Number(s)
4.1 Is the source population described?				15,16
4.2 Is the planned study population defined in terms of:				
4.2.1 Study time period?				11
4.2.2 Age and sex?				15
4.2.3 Country of origin?				
4.2.4 Disease/indication?				16
4.2.5 Co-morbidity?				16
4.2.6 Seasonality?				
4.3 Does the protocol define how the study population will be sampled from the source population? (e.g. event or inclusion/exclusion criteria)				16

Comments:

--

Section 5: Exposure definition and measurement	Yes	No	N/A	Page Number(s)
5.1 Does the protocol describe how exposure is defined and measured? (e.g. operational details for defining and categorising exposure)				17

Section 5: Exposure definition and measurement	Yes	No	N/A	Page Number(s)
5.2 Does the protocol discuss the validity of exposure measurement? (e.g. precision, accuracy, prospective ascertainment, exposure information recorded before the outcome occurred, use of validation sub-study)				
5.3 Is exposure classified according to time windows? (e.g. current user, former user, non-use)				
5.4 Is exposure classified based on biological mechanism of action and taking into account the pharmacokinetics and pharmacodynamics of the drug?				
5.5 Does the protocol specify whether a dose-dependent or duration-dependent response is measured?				19

Comments:

Section 6: Endpoint definition and measurement	Yes	No	N/A	Page Number(s)
6.1 Does the protocol describe how the endpoints are defined and measured?				18,19
6.2 Does the protocol discuss the validity of endpoint measurement? (e.g. precision, accuracy, sensitivity, specificity, positive predictive value, prospective or retrospective ascertainment, use of validation sub-study)				

Comments:

Section 7: Confounders and effect modifiers	Yes	No	N/A	Page Number(s)
7.1 Does the protocol address known confounders? (e.g. collection of data on known confounders, methods of controlling for known confounders)				17
7.2 Does the protocol address known effect modifiers? (e.g. collection of data on known effect modifiers, anticipated direction of effect)				

Comments:

Section 8: Data sources	Yes	No	N/A	Page Number(s)
8.1 Does the protocol describe the data source(s) used in the study for the ascertainment of:				
8.1.1 Exposure? (e.g. pharmacy dispensing, general practice prescribing, claims data, self-report, face-to-face interview, etc.)				17,18
8.1.2 Endpoints? (e.g. clinical records, laboratory markers or values, claims data, self-report, patient interview including scales and questionnaires, vital statistics, etc.)				17,18
8.1.3 Covariates?				
8.2 Does the protocol describe the information available from the data source(s) on:				
8.2.1 Exposure? (e.g. date of dispensing, drug quantity, dose, number of days of supply prescription, daily dosage, prescriber)				17,18
8.2.2 Endpoints? (e.g. date of occurrence, multiple event, severity measures related to event)				17,18
8.2.3 Covariates? (e.g. age, sex, clinical and drug use)				

Protocol for non-interventional studies based on existing data

BI Study Number 1200.270

c09038525-01

Proprietary confidential information © 2016 Boehringer Ingelheim International GmbH or one or more of its affiliated companies

Section 8: Data sources	Yes	No	N/A	Page Number(s)
history, co-morbidity, co-medications, life style, etc.)				
8.3 Is a coding system described for:				
8.3.1 Diseases? (e.g. International Classification of Diseases (ICD)-10)				
8.3.2 Endpoints? (e.g. Medical Dictionary for Regulatory Activities (MedDRA) for adverse events)				
8.3.3 Exposure? (e.g. WHO Drug Dictionary, Anatomical Therapeutic Chemical (ATC) Classification System)				
8.4 Is the linkage method between data sources described? (e.g. based on a unique identifier or other)				

Comments:

Section 9: Study size and power	Yes	No	N/A	Page Number(s)
9.1 Is sample size and/or statistical power calculated?				18,19

Comments:

Section 10: Analysis plan	Yes	No	N/A	Page Number(s)
10.1 Does the plan include measurement of excess risks?				
10.2 Is the choice of statistical techniques described?				19
10.3 Are descriptive analyses included?				19
10.4 Are stratified analyses included?				
10.5 Does the plan describe methods for adjusting for confounding?				19
10.6 Does the plan describe methods addressing effect modification?				

Comments:

Section 11: Data management and quality control	Yes	No	N/A	Page Number(s)
11.1 Is information provided on the management of missing data?				20
11.2 Does the protocol provide information on data storage? (e.g. software and IT environment, database maintenance and anti-fraud protection, archiving)				21
11.3 Are methods of quality assurance described?				21
11.4 Does the protocol describe possible quality issues related to the data source(s)?				
11.5 Is there a system in place for independent review of study results?				

Comments:

Protocol for non-interventional studies based on existing data

BI Study Number 1200.270

c09038525-01

Proprietary confidential information © 2016 Boehringer Ingelheim International GmbH or one or more of its affiliated companies

Section 12: Limitations	Yes	No	N/A	Page Number(s)
12.1 Does the protocol discuss: 12.1.1 Selection biases? 12.1.2 Information biases? (e.g. anticipated direction and magnitude of such biases, validation sub-study, use of validation and external data, analytical methods)				23
12.2 Does the protocol discuss study feasibility? (e.g. sample size, anticipated exposure, duration of follow-up in a cohort study, patient recruitment)				15
12.3 Does the protocol address other limitations?				20

Comments:

--

Section 13: Ethical issues	Yes	No	N/A	Page Number(s)
13.1 Have requirements of Ethics Committee/Institutional Review Board approval been described?				24
13.2 Has any outcome of an ethical review procedure been addressed?				
13.3 Have data protection requirements been described?				21,24

Comments:

--

Section 14: Amendments and deviations	Yes	No	N/A	Page Number(s)
14.1 Does the protocol include a section to document future amendments and deviations?				10

Comments:

--

Section 15: Plans for communication of study results	Yes	No	N/A	Page Number(s)
15.1 Are plans described for communicating study results (e.g. to regulatory authorities)?				
15.2 Are plans described for disseminating study results externally, including publication?				30

Comments:

--

Name of the main author of the protocol: _____

Date: 26/2/2016

Signature: _____

[figure not shown]

## 1 Methods for calculation of derived variables

Age at registration: Year of registration [patient.birthyear] – Year of birth [registration.registered\_at]

Drug-related AE: All AE with relationship to Gi(I)otrif® [ae.gilotref\_relation\_1='yes']

Time on treatment: Date of last administration [endofobservation.date] - Date of first administration of Gi(I)otrif® [baseline.date]. For patients still on treatment, time on treatment will be censored at the date of data collection.

Time to progression (TTP): First date of progression [min(endofobservation.radio\_date, endofobservation.clinic\_date)] - Date of first administration of Gi(I)otrif® [baseline.date]. Patients not known to have a progression will be censored with the date of last contact. For patients still on treatment and without progression, time to progression will be censored at the date of data collection. For patients who stopped treatment and without progression or progression date missing, time to progression will be censored on the last contact date.

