	
 1. EGFR mutated (common mutations), TKI-naïve advanced NSCLC treated with Gi(1)otrif[®] as the first-line treatment for NSCLC within the approved label will be included 2. Patients treated within clinical trials are excluded 3. Patients still on treatment with Gi(1)otrif[®] will be excluded unless treatment period is ≥ 6 months
Variables:	
Primary outcomes:
 
Safety outcomes:
 
Percentage of subjects with adverse drug reactions by severity class
 
Effectiveness outcomes:
 
Time on treatment with Gi(1)otrif[®]
 
Time to progression with Gi(1)otrif[®]

Data sources:	NIS based on existing data from medical records of patients.
Study size:	At least 200 patients. ≥ 200 patients are planned based on feasibility aspects and assumptions.
Data analysis:	
Safety data will be analysed in a descriptive manner. Incidence and severity of adverse drug reactions will be summarized and displayed. For patients who have dose modifications, frequency and severity of the most common AEs pre- and post-dose modification will be summarized and displayed.
 
For effectiveness analysis, both time on treatment and time to progression will be estimated using Kaplan-Meier method, and the median along with two-sided 95% CI will be displayed (use the Greenwood's formula for estimation of standard errors). Log-rank test will be applied to compare between patients with and without dose modifications.

Milestones:	
Start of data collection in May 2016
 
End of data collection in December 2016
 
Final report of study results expected in March 2017

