9.2.1 Selection of study population

Site selection:

Sites in countries with launch dates prior to 1st Jan 2015 and known to prescribe Gi(l)otrif[®] on a regular basis will be chosen. Asian and Non-Asian countries will be included.

Inclusion criteria:

All consecutive patients will be included if all the following criteria are present:

- Age \geq 18 years

Protocol for non-interventional studies based on existing data

BI Study Number 1200.270

c09038525-01

Proprietary confidential information © 2016 Boehringer Ingelheim International GmbH or one or more of its affiliated companies

- Patients with EGFR mutation (common mutations), TKI-naïve advanced NSCLC, treated with Gi(l)otrif[®] as the first-line treatment for NSCLC within the approved label
- Signed and dated written informed consent per regulations. (Exemption of a written informed consent for retrospective observational studies in some countries per local regulations and legal requirements.)

Exclusion criteria:

Patient won't be included if any of the following criteria is present:

- Any contraindication to Gi(l)otrif[®] as specified in label.
- Patients with uncommon mutations are excluded as uncommon mutations are not within label in all participating countries (e.g. USA).
- Patients still on treatment with Gi(l)otrif[®] will be excluded unless treatment period is ≥ 6 months.
- Patients treated with Gi(l)otrif[®] within an interventional trial.

A log of all patients included into the study will be maintained in the ISF at the investigational site.

Patients treated with Gi(l)otrif[®] in interventional trials are excluded to ensure the non-interventional setting of this study. The threshold of ≥ 6 months treatment with Gi(l)otrif[®] for patients being still on treatment was chosen to avoid early censoring and enable collection of mature data on ADRs and treatment duration. However, patients who stopped Gi(l)otrif[®] < 6 months will be included to avoid bias. All patients fulfilling inclusion and exclusion criteria from a site will be entered to avoid bias. The maximum of 15 patients per site was chosen to avoid bias by high proportion of patients coming from one site.

BI reserves the right to discontinue the study overall or at a particular study site at any time for the following reasons:

1. Failure to meet expected enrolment goals overall or at a particular study site.

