9.7 DATA ANALYSIS

9.7.1 Main analysis

All collected data will be analysed separately for patients starting with 40mg and \leq 30mg. Although due to anticipated low sample size in patients starting with \leq 30mg, it will be mainly for exploratory purpose. Baseline demographics will be analysed with descriptive statistics (N, median, mean, 25%, 75% percentile, SD) and compared descriptively between patients who have dose modifications within the first 6 months of Gi(l)otrif[®] treatment and those who do not. All the demographics, safety and efficacy data from this study in real-world setting will be compared with data from LUX-Lung 3 trial in descriptive manner.

Analysis of Safety:

[figure not shown]
Safety analysis will include all patients treated with Gi(l)otrif[®] and be descriptive in nature. Incidence and severity of ADRs according to Common Terminology Criteria for Adverse Events (CTCAE) criteria (version 4.0) ([R15-5988](#)) when available will be summarized and displayed in number/percentage. For patients who had Gi(l)otrif[®] dose modifications within the first 6 months of Gi(l)otrif[®] treatment, frequency and severity of the common ADRs pre- and post-dose modification will be analysed (\geq 40mg vs $<$ 40mg; and \geq 30mg vs $<$ 30mg). Missing or incomplete ADR dates will be imputed according to BI internal SOPs.

Analysis of Effectiveness:

Effectiveness analysis will include all patients treated with Gi(l)otrif[®]. Time on treatment is from the date of first dose of Gi(l)otrif[®] treatment to the date of last dose of Gi(l)otrif[®] treatment. Time to progression is from the date of first dose of Gi(l)otrif[®] treatment to the earliest date of documented progression (clinical, radiographic or both clinical/radiographic progression) or death. Time on treatment and time to progression will be estimated using Kaplan-Meier method, and the median along with two-sided 95% CI will be displayed (use the Greenwood's formula for estimation of standard errors). Log-rank test will be applied to compare between patients with and without dose modifications. Time on treatment and time to progression will be compared between patients who dose reduced to $<$ 40 mg within the first 6 months of Gi(l)otrif[®] treatment and those who remained on Gi(l)otrif[®] 40 mg once daily. This is in analogy to the analysis made on LUX-Lung 3 where a cut-off of 6 months was used as most dose reductions occur during this time.

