In the analyses of the two time-to-event endpoints, missing or incomplete data are managed by standard survival analysis techniques. For patients still on treatment, time on treatment will be censored at the date of data collection. For patients still on treatment and without progression, time to progression will be censored at the date of data collection. For patients stopped treatment and without progression/death or progression/death date missing, time to

progression will be censored on the last contact date.

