9.9 LIMITATIONS OF THE RESEARCH METHODS

The generalization and consequently the external validity of the study results, may be limited by the participation in the study of only sites that prescribe Gi(l)otrif[®] on a regular basis to ensure sufficient patient recruitment. Patients treated by investigators with less experience might experience more side effects during their treatment with Gi(l)otrif[®].

Methodological efforts have been taken to minimize selection bias: these efforts include the recommendation to include consecutive patients meeting each of the inclusion criteria and none of the exclusion criteria. In addition, this possible selection bias may be limited by the retrospective aspect of the data collection, data that have been already collected at the time of the study. Linked to this aspect is then the limitation due to data availability. Indeed, no additional data will be collected for the study purpose. So if the data is not available in the patient files, then this will be considered as missing data.

In addition, to reduce error in data collection, a standard study eCRF will be used, ensuring a measure of consistency among the collectors.

Another limitation is coming from the diverse handling of data collection from deceased patients which is allowed without informed consent in some countries but not in all.

However, no country-based analyses will be done. Given the median overall survival (31.6 months in LUX-Lung 3) and that time from launch of Gi(l)otrif to data collection in the participating countries is shorter than the median overall survival (OS) the majority of the patients are expected to be alive.

External validity is provided by the global approach of this study and the broad inclusion criteria but limited to patients treated within the label and at the selected, experienced sites. Internal validity will be given by source data verification.

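### The SAP gives patients still on treatment without progression two TTP censoring dates, and the data-collection date counts unobserved time as progression-free

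*SAP*

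**What the plan says.** SAP section 1 (Methods for calculation of derived variables) has three consecutive sentences on TTP censoring:

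- General: "Patients not known to have a progression will be censored with the date of last contact".
- Still on treatment: "For patients still on treatment and without progression, time to progression will be censored at the date of data collection".
- Stopped treatment: "For patients who stopped treatment and without progression or progression date missing, time to progression will be censored on the last contact date".

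Protocol 9.7.1 has the second and third rules, the third also covering death, but not the general sentence. For the other time-to-event outcome, both documents have one rule: "For patients still on treatment, time on treatment will be censored at the date of data collection".

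Three other places matter. Protocol 9.9 says of the chart review: "Indeed, no additional data will be collected for the study purpose". Protocol 9.2.1 admits patients still on afatinib after at least 6 months; that threshold for patients "being still on treatment was chosen to avoid early censoring". Protocol 9.7.1 reports TTP as a Kaplan-Meier median with a 95% CI, and adds: "Log-rank test will be applied to compare between patients with and without dose modifications".

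**The concern.** There are two linked problems. First, a patient on treatment without progression satisfies both the general sentence and the on-treatment sentence. Two programmers could derive different TTP values from the same record, and each could point to the SAP.

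Second, the data-collection date is when someone reads the chart, not when the patient is assessed. A progression after the last chart entry cannot appear in the data, yet the patient stays in the risk set as event-free until abstraction. This adds person-time in which no event can be recorded. Patients who stopped treatment are censored at last contact and do not have this problem, and the plan does not explain the difference.

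TTP is a primary outcome, and Protocol 9.7.1 sets it descriptively beside LUX-Lung 3. An upward shift in the median would make real-world results look better in that comparison.

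**Working it through.** The documents state no figure that depends on this point, so there is none to reproduce. The check is a comparison of the rules and an illustration of size.

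**Rules side by side (TTP, no progression recorded)**

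| Patient | SAP general sentence | SAP specific sentence | Protocol 9.7.1 |
|---|---|---|---|
| Still on treatment | last contact | data collection | data collection |
| Stopped treatment | last contact | last contact | last contact |

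The two specific sentences already cover both kinds of patient. The general sentence is therefore redundant for those who stopped and in conflict for those still on treatment.

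**Inputs for size.** From Protocol section 7: LUX-Lung 3 median PFS of 11.1 months (all afatinib patients) and 13.6 months (common mutations, the group eligible here). Assumed, because the documents do not give them: exponential TTP; time from first dose to abstraction uniform over a stated range; a gap between last recorded contact and abstraction; progression inside the gap not recorded; every patient without progression still on treatment.

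**Hazard, by hand.** With median 11.1, λ = ln 2 / 11.1 = 0.0624 per month. If a fraction p is censored, observed person-time per patient is (1 − p)/λ. Data-collection censoring adds about p × g, where g is the mean gap. The estimated hazard is then multiplied by [(1 − p)/λ] / [(1 − p)/λ + p·g]. With abstraction 6 to 33 months after first dose and the gap uniform on 0 to 2g, simulation gives p of about 0.35, 0.37 and 0.40:

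- g = 0.75: 10.41 / (10.41 + 0.26) = 0.975, or 2.5% too low.
- g = 1.5: 10.09 / (10.09 + 0.56) = 0.947, or about 5% too low.
- g = 3: 9.61 / (9.61 + 1.20) = 0.889, or about 11% too low. Simulation gives 12%, because patients with long gaps are more often censored.

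**Kaplan-Meier median, by simulation (months, true median 11.1, gap uniform on 0 to 2g)**

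| Mean gap | Last contact | Data collection, follow-up 6–33 | Data collection, follow-up 12–36 |
|---|---|---|---|
| 0.75 | 11.1 | 11.2 to 11.3 | 11.1 |
| 1.5 | 11.1 | 11.5 | 11.1 |
| 3 | 11.1 | 12.2 | 11.3 |

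The shift is about 0.1 to 1.1 months in the first case and 0 to 0.2 in the second. It depends on follow-up because the median uses only the curve up to about 11 months. If everyone has at least 12 months, little of the unobserved time falls that early.

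**True median 13.6, fixed gaps of 1 / 2 / 3 months.** Data-collection censoring gives 14.1 / 14.6 / 15.4 months with 6 to 30 months of follow-up, and 13.7 / 13.9 / 14.1 with 12 to 36. Last-contact censoring returns 13.6 to 13.7 throughout.

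**The case against.** The general sentence can be read as a default that the next two refine. On that reading both documents agree on the data-collection date for patients still on treatment, and the SAP is untidy rather than contradictory. This is a reasonable reading, but the SAP does not state it, and it leaves the unobserved time in place.

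The size may be negligible. With long follow-up or short gaps the shift is near zero. Under the 6-to-33-month assumptions, the median from 200 patients has a sampling SD of about 1.2 months (95% range about 9.0 to 13.7), so shifts of 0.2 or 0.4 months are small beside it. The illustration also treats every patient without progression as still on treatment, although those who stopped are already censored at last contact. All of this stands. It limits the size but does not change the direction.

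The alternative rule is not free of bias either. If progression itself prompts a visit and a chart entry, data-collection censoring is correct and last-contact censoring is slightly low: a true 11.1 reads about 10.9, 10.7 or 10.3 for mean gaps of 0.75, 1.5 or 3 months under the same 6-to-33-month assumptions. This also stands, and is the reason to report both versions.

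The primary objective concerns dose modification. With equal gaps in both groups, an assumed rate ratio of 1.25 stays at 1.25 to 1.26, so harm to the log-rank comparison is not shown.

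**Conclusion.** The point holds in limited form. The overlap of rules and the undefined date are on the face of the text and need no assumption. The upward bias in the TTP median follows if charts are silent between last contact and abstraction. Its size rests on an assumed gap and follow-up: about 0.1 to 1.1 months, or 0 to 0.2, for a true median of 11.1, depending on follow-up.

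A reader might infer three stronger things that the documents do not support:

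- **A third or more of patients are affected.** That fraction comes from simulation. The documents give no fraction still on treatment.
- **The time-on-treatment median is biased in the same way.** That outcome has one rule in both documents, and if the record confirms treatment at abstraction there is no gap. Bias is possible but not quantified.
- **Patients are censored at the 31 December 2016 milestone, adding up to 7 unobserved months.** The Protocol abstract has "End of data collection in December 2016", and section 9.3 uses that endpoint as a documentation cut-off, but the censoring rule uses a different term. This supports asking for a definition, not a bias figure.

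**What to change.** In SAP section 1 and Protocol 9.7.1:

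1. Replace the TTP censoring sentences with one rule for all patients without recorded progression or death: censor at the last documented contact or assessment without progression, on or before the patient's own abstraction date.
2. Define the date of data collection as that per-patient abstraction date.
3. Report TTP censored at the data-collection date as a sensitivity analysis. The two versions bracket the cases where progression does and does not prompt a chart entry.
4. For time on treatment, censor at the last date on which the record documents treatment as ongoing. This may equal the abstraction date.

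The cost is wording in two documents and one extra analysis. Follow-up will be slightly shorter, and the main TTP median may be slightly low if progression prompts chart entries. The sponsor should also check that the eCRF captures the last contact date: the SAP already relies on it, but the variable list in Protocol 9.3 does not include it.
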